6.2.1 Justification of Dose Selection and Efficacy Analysis

In the adult controlled clinical trials for the LVO and EBD indication, the duration of the useful imaging time for LV chamber opacification was 2.5 to 4.5 minutes for a dose of 0.5 to 3.0 mL [OPTISON PI].

McMahon et al conducted rest non-contrast and CE-ECHO in 20 children (9 to 18 years) with limited transthoracic echo windows [McMahon et al. 2005]. OPTISON was administered at a dose of 0.3 mL per injection for children <20 kg and 0.5 mL per injection for those ≥ 20 kg. The EBD was significantly improved in all patients with CE-ECHO and LVEF was measurable in all 20 patients using contrast echo versus only 11 with non-contrast echocardiography. Zilberman et al performed contrast stress echocardiography with OPTISON administration in 22 children (8 months to 19 years; mean age 9.3 ± 3.9 years) [Zilberman et al. 2003]. A dose of 0.1 mL was given for patients ≤ 25 kg, and 0.2 mL for patients > 25 kg. These doses provided adequate opacification of the LV cavity for up to 60 seconds.

Similar to the two publications, OPTISON dose in this study will be administered based on body weight. According to the Centers for Disease Control and Prevention Pediatric Growth Charts [CDC Growth Charts], children > 9 years of age usually weigh > 28 kg and children > 12 years of age usually weigh > 40 kg for both boys and girls in the United States, but weight varies greatly for a specific age. Two dose levels will be tested in each weight cohort: 0.1 or 0.2 mL per injection to children weighing ≥ 20 to ≤ 28 kg, 0.2 or 0.3 mL per injection to those who weigh > 28 to ≤ 40 kg, and 0.2 or 0.4 mL per injection to those who weigh > 40 kg. It is expected that one or more of these dose levels will be able to provide adequate LVO and EBD in these groups of pediatric patients with a limited transthoracic echocardiographic window.

6.2.2 Justification of Safety Monitoring Plan

This study's safety monitoring plan is justifiable and adequate from a safety standpoint:

- The design of the safety plan permits a comparison of the safety response to OPTISON at baseline and post-investigational medicinal product (IMP) administration conditions in the same subject.
- Consideration of a 3-day safety monitoring follow-up permits the evaluation of late-appearing adverse effects that may emerge or progress after the administration of OPTISON.
- The measures used to assess safety are well-defined and reliable, and the proposed safety analyses are adequate to assess the effects of the administration of OPTISON.

6.3 Study Timeframe

The duration of each subject's participation is expected to be up to 3 weeks, including screening (2 weeks), procedure, and safety follow-up (24 hours and 72 hours post OPTISON administration).

The entire subject recruitment phase is expected to last up to 2 years.

6.4 Risks and Benefits to Subjects

Study participants may help future patients by contributing to a knowledge base for further evaluation of the use of OPTISON in pediatric patients with cardiac disease. For some patients participating in the study, the benefit might be detection or more precise evaluation of their cardiac disease.

OPTISON is well tolerated in adults. Adverse reactions to OPTISON are rare and usually of a non-serious nature. In general, the administration of human albumin has been associated with transient altered taste, nausea, flushing, rash, headache, vomiting, chills and fever. The shell of the OPTISON bubble is composed of albumin. Rare anaphylactic reactions have been associated with the administration of human albumin products. The reported adverse events (AEs) following the use of OPTISON in Phase 3 human clinical studies have been mild to moderate with subsequent full recovery.

For further information please refer to the currently approved OPTISON Package Insert [\[OPTISON PI\]](#).

7 SELECTION AND WITHDRAWAL OF SUBJECTS

7.1 Procedures for Enrolment

Investigators are responsible for subject recruitment at their sites. A signed and dated (with time) informed consent form will be obtained from a parent or legal guardian of each study subject prior to study entry or any study-specific procedures. Age-appropriate pediatric assent will be obtained where appropriate. Subjects will be screened for entry through the use of clinical examination and historic assessment. A unique study-related subject number will be assigned at baseline before the unenhanced echocardiography procedure.

7.2 Inclusion Criteria

Subjects may be included in the study if they meet all of the following criteria:

- (1) The subject is between ≥ 9 and <18 years of age and weighs ≥ 20 kg.
- (2) The subject is clinically indicated to undergo a transthoracic echocardiogram.
- (3) The subject has a suboptimal non-contrast echocardiogram defined as ≥ 2 contiguous segments in any given view that cannot be visualized.
- (4) The subject is able to comply with study procedures.
- (5) A parent or legal guardian of the subject has signed and dated an informed consent form, and age-appropriate pediatric assent has been obtained where appropriate.
- (6) Post-menarchal female subjects must have a negative urine pregnancy test at screening and at pre-dose on the day of OPTISON administration.
- (7) Post-menarchal female subjects must be practicing abstinence, or be using an effective form of birth control (e.g., intrauterine device, oral contraceptives, contraceptive implants or injections, diaphragm with spermicide, cervical cap, or consort use of condom) for at least 30 days before being enrolled in the study.

7.3 Exclusion Criteria

Subjects must be excluded from participating in this study if they meet any of the following criteria:

- (1) The subject was previously enrolled in this study.
- (2) The subject has received an IMP within 30 days before or is scheduled to receive one from time of entry into this study until completion of the follow-up period proposed for this study.

- (3) The subject has a known or suspected hypersensitivity to any of the components of OPTISON, blood, blood products, or albumin.
- (4) The subject has pulmonary hypertension or unstable cardiopulmonary conditions.
- (5) The subject has severe liver disease based on medical history.
- (6) The subject had a recent (<6 months) neurological event.
- (7) The subject presents any clinically active, serious, life-threatening disease, with a life expectancy of less than 1 month or where study participation may compromise the management of the subject or other reason that in the judgment of the investigator makes the subject unsuitable for participation in the study.
- (8) The subject is a pregnant or lactating female, or is a female of childbearing potential not using an acceptable form of birth control (negative urine pregnancy test also required).

7.4 Withdrawal and Termination Criteria

7.4.1 Subject Withdrawal

During the conduct of the study, the sponsor will review the safety data for trends and signals that would indicate the need for withdrawal of a subject. If a subject undergoes an intervention or has a significant change in disease status between the administration of OPTISON and the completion of study follow-up, the subject will be withdrawn from the study.

In accordance with the Declaration of Helsinki, each subject is free to withdraw from the study at any time. Investigator(s) also have the right to withdraw subjects from the study in the event of illness, AEs, or other reasons concerning the health or well-being of the subject, or in the case of lack of co-operation.

Should a subject decide to withdraw after administration of OPTISON, or should the investigator(s) decide to withdraw the subject, all efforts will be made to complete and report the observations up to the time of withdrawal as thoroughly as possible. A complete final evaluation at the time of the subject's withdrawal should be made and an explanation given of why the subject is withdrawing or being withdrawn from the study.

The reason for withdrawal must be noted in the Case Report Form (CRF). If the reason for withdrawal is a serious adverse event (SAE), monitoring will continue until the outcome is evident. The specific event or test result(s) must be recorded in the CRF.

If a subject is withdrawn before completion of CE-ECHO, the subject will be replaced. The replaced subject will be assigned a new subject number.

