10.3.5 Adverse Events

The AE profile of OPTISON has not yet been established in pediatric patients. Study personnel must remain vigilant for the occurrence of AEs, particularly those that may be life threatening. Personnel who are trained in the management of acute anaphylaxis and other emergencies and who have access to appropriate clinical supplies must be immediately available for at least 30 minutes to observe for possible anaphylactoid reactions after dosing. Treatment of SAEs should be primarily supportive of vital functions.

An AE is defined as any untoward medical occurrence in a patient or clinical investigation subject which does not necessarily have to have a causal relationship with the study treatment. AEs will be asked for from time of informed consent through 72 ±8 hours after the last administration of contrast agent.

A TEAE is any unfavorable and unintended sign, symptom, or disease temporally associated with the use of OPTISON, whether or not considered related to that product. Only symptoms/signs that begin or worsen in severity and/or frequency after OPTISON administration/use will be recorded as TEAEs in the CRF.

The subjects will be closely observed and questioned for any kind of AE during the study procedures and at follow-up appointments throughout the study period with non-leading questioning (e.g., "How do you feel?"). The subjects will be instructed to immediately report any symptoms and signs to the study staff (i.e., between formal observations).

See section [10.3.8](#) for documentation of SAEs in the CRF.

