10.3.8 Adverse Event and Serious Adverse Event Reporting

All AEs should be recorded using acceptable diagnoses, if possible. If an AE has already been reported it is not necessary to report each individual sign and symptom of that AE as a separate AE. For example, if myocardial infarction is reported as an AE, there is no need to report elevated creatine phosphokinase and abnormal ECG, or other related signs, symptoms, or laboratory values as separate AEs. However, if both occurred in isolation and myocardial infarction was not diagnosed, then each event would be reported as an AE.

The intensity of all AEs will be graded as mild, moderate, or severe using the following definitions:

Mild:	Tolerable.
Moderate:	Interferes with normal activity.
Severe:	Incapacitating (causes inability to perform usual activity or work).

The investigator will be instructed to closely monitor each subject who experiences an AE (whether ascribed to the IMP or not) until the outcome of the AE has been determined.

Both the investigator and GE Healthcare will perform a causality assessment on any AE, to assess whether or not there is a reasonable possibility (evidence to suggest) that the IMP caused the event.

SAEs will be recorded in the CRF and on the SAE reporting form if they occurred as follows:

- After a subject first signed informed consent and throughout the subject's follow-up period*, whether or not considered related to the OPTISON, and
- After the subject's follow-up period, and for which a causal relationship to the OPTISON is a reasonable possibility (evidence to suggest) that the OPTISON caused the event. Causality evaluation for any AE shall be documented.

(*Follow-up period is defined as the protocol-stipulated period of 72±8 hours after administration of the IMP or, for subjects prematurely withdrawn from a study, the duration of a subject's participation.)

All serious and non-serious AEs must be followed for a final outcome until the end of the follow-up period. An outcome of "unknown" is not considered to be an acceptable final outcome. An outcome of "not yet resolved" is an acceptable final outcome for non-serious AEs at the end of a subject's participation in a study, and for SAEs at database lock.

The sponsor will report all SAEs to local health authorities, IECs/IRBs and investigators as required by local regulations and sponsor standard operating procedures (SOPs).

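### After a withdrawal required by protocol 7.4.1, the protocol gives conflicting answers on whether new adverse events are still sought to 72 hours

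*Protocol*

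**What the plan says.** Protocol 7.4.1 sets a mandatory rule. It opens "If a subject undergoes an intervention or has a significant change in disease status" and continues "between the administration of OPTISON and the completion of study follow-up, the subject will be withdrawn from the study". The withdrawal is from the study and no discretion is given. For a child withdrawn after dosing, "all efforts will be made to complete and report the observations up to the time of withdrawal as thoroughly as possible", with a final evaluation at that time. One exception follows: "If the reason for withdrawal is a serious adverse event (SAE), monitoring will continue until the outcome is evident".

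A note to the SAE-recording rules in protocol 10.3.8 shortens the follow-up period to the child's time in the study "for subjects prematurely withdrawn from a study, the duration of a", where other children have the full 72±8 hours. The same section then uses that period as a limit: "All serious and non-serious AEs must be followed for a final outcome until the end of the follow-up period".

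Elsewhere the window has no exception for withdrawn children. Protocol 10.3.5 says "AEs will be asked for from time of informed consent through 72", with a margin of 8 hours either way, counted from the last dose. Protocol 9.4 and Table 2 schedule telephone contacts at 24±4 and 72±8 hours. Protocol 6.2.2 justifies the three-day window by the need to see late-appearing effects.

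On analysis, SAP 4.1.1 puts every dosed child in the Safety population, and SAP 6.5.2.1 reports treatment-emergent AEs (TEAEs) as numbers and percentages of subjects. Protocol 12.1 and SAP section 5 impute nothing for missing follow-up.

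**The concern.** The trigger for withdrawal is itself a clinical event after dosing. If withdrawal closes the safety window, observation stops because of what happened to the child, and the late events that the three-day window is meant to catch would no longer be actively sought. A crude percentage over all dosed children would then count an unseen event as no event.

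Safety is a secondary objective, and protocol 10.3.5 says that the pediatric AE profile is not yet established. Two sites could also act differently in good faith. One would stop contact at withdrawal on the strength of 10.3.8; the other would make both calls on the strength of 9.4 and 10.3.5.

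**Working it through.** The plan gives no withdrawal, intervention or event rate, so there is no figure to reproduce. The check is textual, followed by an illustration under stated assumptions.

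**1. Does the window close at withdrawal?**

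| Source | Reading |
|---|---|
| Protocol 7.4.1 | Observations up to withdrawal, plus a final evaluation |
| Protocol 10.3.8 | Follow-up period ends with participation |
| Protocol 10.3.5 | AEs collected to 72±8 h, no exception |
| Protocol 9.4, Table 2 | Calls at 24 h and 72 h, no exception |

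Neither document says that the calls continue after a 7.4.1 withdrawal, and neither says that they stop. The passages conflict.

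**2. What is still followed or recorded after withdrawal?**

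- An SAE that was the reason for withdrawal is monitored until its outcome is evident (7.4.1).
- AEs that are serious, related to the drug or to study procedures, or the cause of discontinuation are followed up by the investigator (10.3.6).
- An AE already under way, whatever its cause, is monitored to its outcome (10.3.8).
- A later SAE is recorded if there is a reasonable possibility that OPTISON caused it (10.3.8).

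**3. What is left uncovered?** None of these provisions requires a contact to look for new events. The gap is new non-serious AEs, new SAEs with no reasonable possibility of causality, and remaining scheduled assessments. By Table 2, vital signs, ECG and physical examination finish 1 hour after the last dose. A later withdrawal therefore affects only the two calls, with the AE and concomitant-medication information they collect.

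**4. How does the gap reach the tables?** A child whose withdrawing event was recorded as a TEAE already counts once in overall TEAE incidence. The downward bias therefore applies to two quantities:

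- the rate of a specific late event; and
- overall incidence, where a child is withdrawn with no recorded AE.

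The second case is foreseeable. Protocol 10.3.8 says that a newly detected pre-existing abnormality need not be reported as an AE or SAE even if it leads to hospitalization or surgery. If that surgery falls within the window and counts as an intervention, a term that 7.4.1 does not define, the child is withdrawn without an AE and the SAE-monitoring exception does not apply.

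**5. Illustration of precision.** Assume 30 dosed children. The SAP's 30 is a count of evaluable subjects, not of the Safety population. Exact two-sided 95% upper limits are:

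- 0/30: 1 − 0.025^(1/30) = 11.6%.
- 1/30: solve (1−p)^30 + 30p(1−p)^29 = 0.025. At p = 0.1722 the terms are 0.0035 + 0.0215 = 0.0250, so the limit is 17.2%.

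**6. Illustration of bias.** Let w of N dosed children be withdrawn under the rule. Suppose the risk of a new non-serious TEAE after that time is q in them, all unseen, and r = 5% in the rest. None of these values is in the documents.

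- True risk = [wq + (N−w)r]/N
- Observed risk = (N−w)r/N
- Proportion understated = 1 − observed/true

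| N | w | True risk (q = 20% to 50%) | Observed | Understated by |
|---|---|---|---|---|
| 30 | 1 | 5.5% to 6.5% | 4.8% | 12% to 26% |
| 30 | 3 | 6.5% to 9.5% | 4.5% | 31% to 53% |
| 50 | 1 | 5.3% to 5.9% | 4.9% | 8% to 17% |
| 50 | 3 | 5.9% to 7.7% | 4.7% | 20% to 39% |

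If q = r, the understatement is w/N, or 3.3% for 1 of 30. With no such withdrawals it is zero.

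**The case against.** The strongest reply is that the shortened definition in 10.3.8 is a note attached to SAE recording, while the rule that governs AE collection, 10.3.5, runs to 72±8 hours for everyone. On that reading nothing is lost. This has force, and it is why the point is a conflict to reconcile rather than an established loss. It does not remove the problem, because 10.3.8 reuses the same period for following AEs generally and 7.4.1 speaks of observations up to withdrawal.

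A second reply is that the safeguards in 7.4.1, 10.3.6 and 10.3.8 cover the events that matter most. That also largely stands. A reader might infer that monitoring continues only when an SAE causes the withdrawal; 10.3.6 and 10.3.8 show otherwise.

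A third reply is that a child withdrawn for clinical worsening will usually already be a recorded TEAE, and that 10.3.7 separately has events leading to an intervention reported. A reader might infer that overall TEAE incidence would fall from 1/30 to 0/30 in such a case. It would not. The illustration applies only to a specific late event or to a child withdrawn with no recorded AE.

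**Conclusion.** The point holds in a limited form. Sections 7.4.1 and 10.3.8 together allow safety observation to end on a post-dose clinical event, against 9.4 and 10.3.5. The exposed data are newly arising non-serious AEs, new SAEs with no reasonable possibility of causality, and any remaining scheduled assessments. Because the denominator keeps every dosed child, any bias from unseen events is downward.

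The size is unknown. The limits of 17.2% and 11.6% assume 30 dosed children and one missed child, and the bias table rests on assumed rates.

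A reader might go further and conclude that 72-hour data are cut short in the sickest children. The documents do not support that. No passage says that the calls stop, the trigger on disease is a significant change rather than any change, unstable cardiopulmonary conditions are excluded at entry (7.3), and no rate shows who would be withdrawn. A higher later risk in these children is a reasonable inference from the trigger and no more than that.

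The matter should be corrected because the remedy is cheap and removes a possible outcome-dependent loss. It does not bear on the primary efficacy analysis.

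**What to change.** Reconcile the passages in three places:

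- **Protocol 7.4.1:** state that withdrawal after dosing does not end collection of AEs and SAEs, and that the scheduled 24-hour and 72-hour calls are still made unless consent or assent is withdrawn.
- **Protocol 10.3.8:** narrow the shortened follow-up definition to withdrawal of consent or assent. Deleting it outright would leave children whose consent is withdrawn with no defined SAE-recording period.
- **SAP 6.2 or 6.5:** report the number of dosed children with less than 72 hours of follow-up, alongside the withdrawals and reasons already planned.

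The cost is a short protocol amendment and one added line in a SAP table. The calls are already in the schedule. This concerns data collection only; no view is taken on when a child should be withdrawn or treated.

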7.4.2 Study or Site Termination

GE Healthcare is committed to complete subject enrolment in approximately 2 years. However, if after one year, <10% of the 50 subjects have been enrolled at 12 sites, additional study modifications or study termination will be considered. The sponsor reserves the right to terminate the study at any time.

Should termination be necessary, both the sponsor and the investigators will ensure that adequate consideration is given to the protection of the subjects' interest. Termination of the study will be considered in the event of a significant safety finding occurring at any time during the conduct of the study.

Investigators have the responsibility to comply with International Council for Harmonisation (ICH) E6-Good Clinical Practice (GCP) guidance. The sponsor, the Institutional Review Board (IRB)/Independent Ethics Committee (IEC), or the health authorities may terminate a center for the following (but not limited to) reasons:

- (1) Failure of the investigator to comply with pertinent ICH E6-GCP guidelines and regulations.
- (2) Occurrence of serious protocol violations.
- (3) Submission of knowingly false information from the research facility to the sponsor, clinical monitor, or other party involved in the study.
- (4) Failure of the investigator to enroll subjects into the study at an acceptable rate as agreed with the sponsor.
- (5) Repeated failure to have imaging data transferred to the sponsor or the CRF completed and ready for review by the sponsor in the agreed time frame.

8 TREATMENT OF SUBJECTS

Each investigator is responsible for ensuring that deliveries of IMP and other study materials from the sponsor are correctly received, recorded, handled, and stored safely and properly in accordance with all applicable regulatory guidelines, and used in accordance with this protocol.

All IMP containers (opened, unopened, or empty) must be returned to the sponsor or destroyed on site after the study and overall drug accountability have been completed by the sponsor or representative. A list of IMP(s) and other materials that were returned, or destroyed, must be prepared and signed by the principal investigator or designee. If there are any discrepancies, an explanation for these should also be provided.

8.1 Investigational Medicinal Product

8.1.1 OPTISON

OPTISON (Perflutren Protein-Type A Microspheres Injectable Suspension, [USP]) is a sterile non-pyrogenic suspension of perflutren-containing microspheres (5.0 to 8.0×10^8 /mL with a mean diameter range of 3.0 to 4.5 μm) of heat-treated human serum albumin with perflutren for contrast enhancement during the indicated ultrasound imaging procedures. The approximate amount of perflutren gas in each milliliter of OPTISON is 0.19 mg corresponding to 7 μL . The vial contains a clear liquid lower layer and a white upper layer that, after resuspension by gentle mixing, provides a homogeneous, opaque, milky-white suspension for intravenous injection. OPTISON will be provided in 3-mL vials for single use. OPTISON should be stored refrigerated at 2°C to 8°C (36°F to 46°F). Investigators must follow the package insert instruction to prepare and administer OPTISON.

In adults, the recommended dose of OPTISON ranges from 0.5 to 3.0 mL injected into a peripheral vein with the maximum total dose not exceeding 8.7 mL in any one patient. However, there is no established dosage for children. For this study, the dose information is based on 2 publications using OPTISON in pediatric echocardiography (see Section 6.2.1). Each patient will receive 2 different doses of OPTISON administration for CE-ECHO; the actual doses of OPTISON will be based on pediatric body weight of ≥ 20 to ≤ 28 kg, > 28 to ≤ 40 kg, and > 40 kg and up to 3 injections per dose level are allowed for acquiring different imaging views (Table 1). According to the low volume of OPTISON required for these children, the volume of OPTISON will be diluted within the same volume of saline to facilitate the injection.

Table 1 OPTISON Dosing Table

Body weight (kg)	Dose/injection (mL) Dose level 1	Dose/injection (mL) Dose level 2	Total dose (mL) not to exceed (3 injections/dose level)
≥ 20 to ≤ 28	0.1	0.2	1.0
> 28 to ≤ 40	0.2	0.3	1.5
> 40	0.2	0.4	1.8

The contrast will be administered as a slow bolus at a steady rate of approximately 0.05 mL per second for contrast-enhanced echocardiographic imaging followed by a 5.0 mL slow injection of saline. Injections should be at least 10 minutes apart to allow for clearance of the previous dose.

